6.5. Justification of sample size

The planned sample size for the PIVENS trial is 240 patients with equal allocation to each of the three treatment groups (80 per group).

We based the sample size estimates on a two-group, binomial comparison of the proportions of patients satisfying the primary outcome, improvement in the histologic activity score (defined in Section 6.2) over the course of treatment. Since PIVENS is a three group trial with two primary hypotheses, we assume that the two primary comparisons, pioglitazone vs. placebo and vitamin E vs. placebo, require the same sample size and reduce the type I error from 0.05 to 0.025 (Bonferroni correction). Expected proportions improved were approximated using pilot data from a 48-week pioglitazone study ([name] and [name], personal communication) and from the placebo group in a two-year randomized trial of Urso vs. placebo ([name], personal communication). Currently, there are no available data to estimate the response in vitamin E, which is assumed, for purposes of planning the trial, to be the same as for pioglitazone.

41

The sample calculations were performed using the nQuery Advisor 5.0 (67) software using the formula:

$$n = \frac{\left[z_{1-\alpha/2}\sqrt{2\overline{\pi}(1-\overline{\pi})} + z_{1-\beta}\sqrt{\pi_1(1-\pi_1) + \pi_2(1-\pi_2)}\right]^2}{(\pi_1 - \pi_2)^2}$$

where,

- n = sample size per group
- π_1 = expected proportion improved in placebo group (assumed=0.14)
- π_2 = expected proportion improved in pioglitazone or vitamin E group (0.40)
- $\overline{\boldsymbol{\pi}}$ = average of π_1 and π_2
- α = Two-sided type I error (0.025, Bonferroni corrected for two comparisons)
- β = Type II error (0.10; i.e., 90% power)

The number per group, using the above formula is 71. Inflating this number by the 10% expected missing data rate yields approximately 80 patients per group, or a total of 240 for the trial.

6.6. Interim analysis

An independent Data and Safety Monitoring Board (DSMB), appointed by the NIDDK, is responsible for approving the protocol for the PIVENS trial and for monitoring the accumulated interim data as the trial progresses to ensure patient safety and to review efficacy. The DSMB is a multidisciplinary group with a written charge provided by the NIDDK. The DSMB reports to the NIDDK, which will, in turn, communicate DSMB recommendations to the investigators, as appropriate. The DSMB meets in person to approve the protocol. After the trial commences, the DSMB meets twice a year to review data or other issues – once in person and once by telephone conference. The DSMB may request more frequent meetings if necessary to fulfill its charge. It may also request additional safety reports on a more frequent basis. For example, all serious adverse events are reported to the DSMB for their consideration and recommendations as they occur.

Interim data on safety measures requested by the DSMB are reviewed at each of the scheduled semi-annual full meetings. Two additional written safety reports will be reviewed by the DSMB between scheduled full meetings. Serious adverse events will be reviewed by the DSMB as they occur with the option of a teleconference discussion if any DSMB member so requests.

The DSMB will review quarterly reports by masked treatment groups of incident hepatotoxicities, as well as counts of patients who required more frequent liver function testing due to

42

rises in ALT levels of more than 1.5 times baseline ALT or beyond 250 U/L. The DSMB will also examine the trends in ALT or AST levels for each patient who experiences a rise in ALT.

The DSMB reviews one planned interim analysis of the primary outcome measure. O'Brien-Fleming statistical stopping guidelines for efficacy apply. This interim efficacy analysis will occur when approximately 50% of the data are complete or when approximately 120 of the 240 patients have completed baseline and 96 week biopsies.

The DSMB also reviews the overall progress of the trial in terms of recruitment and data quality and makes a formal recommendation to the NIDDK at the end of each scheduled meeting as to whether the trial should continue unmodified, continue with protocol modifications, or be stopped.

7. Human subjects issues

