5.8.1.1. Safety issues related to thiazolidinediones

• Hepatotoxicity: The first generation TZD, troglitazone, was associated with idiosyncratic hepatotoxicity, and very rare cases of liver failure, liver transplantation, and death. Troglitazone has been withdrawn from clinical use. The second-generation thiazolidinediones appear to be significantly less hepatotoxic. A review of risk of hepatotoxicity associated with second-generation TZD agents is provided in section 2.4. We intend to minimize the risk of hepatotoxicity (or its consequences) (a) by closely monitoring the aminotransferase levels during the study period (at 2, 4, 8, 12, 16, 24, 32, 40, 48, 56, 64, 72, 80, 88, 96, and 120 weeks after randomization), (b) by discontinuing study medication in patients with severe hepatotoxicity (defined as ALT or AST greater than 10 times the ULN in the local lab OR absolute AST or ALT greater than 500 U/L OR serum total bilirubin at least 2.5 mg/dL and at least half of it is direct bilirubin), (c) by avoiding the other potential hepatotoxic agents, and (d) by instructing the patients about self-identification of symptoms associated with hepatotoxicity (i.e., yellow eyes, dark urine, unexplained anorexia, asthenia, or right upper quadrant abdominal pain).

Those who exhibit ALT or AST elevation that is not to the extent described above but who develop a 1.5-fold or greater elevation in ALT or AST from their baseline value and

absolute ALT or AST greater than 250 U/L OR total bilirubin at least 1.5 mg/dL and at least half of it is direct bilirubin OR develop symptoms suggestive of acute hepatotoxicity (i.e., jaundice, nausea, vomiting, abdominal pain, fatigue, anorexia, dark urine) will have their liver biochemistries checked on a weekly basis. If ALT, AST, and/or bilirubin levels decline or stabilize, subjects will have their liver biochemistries checked monthly for 3 months and then according to the protocol schedule. If ALT or bilirubin continues to rise on two consecutive measurements following the initial rise in ALT, AST or bilirubin or if the patient develops symptoms of hepatotoxicity, subjects will be considered to have developed significant hepatotoxicity and the study medication will be discontinued indefinitely.

Patients in whom the study medication has been discontinued due to significant hepatotoxicity will be followed according to the protocol and will be offered a liver biopsy at the conclusion of the study.

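### Section 6.6 limits the DSMB's count of extra liver testing to ALT rises, although 5.8.1.1 also starts weekly testing for AST and bilirubin

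*Protocol*

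**What the plan says.** Two sections of the protocol deal with liver signals below the severe stopping limits.

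**Section 5.8.1.1 decides who is tested weekly.** It is addressed to "Those who exhibit ALT or AST elevation that is not to the extent described above but who develop a 1.5-fold or greater elevation" of either enzyme over the patient's own starting value. An *and* joins this to the absolute limb, after which comes the bilirubin route: "absolute ALT or AST greater than 250 U/L OR total bilirubin at least 1.5 mg/dL and at least half of it is direct bilirubin". Symptoms suggestive of acute hepatotoxicity are a further route. Above this tier is the severe stop: ALT or AST above 10 times the local upper limit of normal (ULN), either enzyme above 500 U/L, or a bilirubin limit, "serum total bilirubin at least 2.5 mg/dL and at least half of it is direct bilirubin". Within the tier, study drug is stopped for a continuing rise ("If ALT or bilirubin continues to rise on two consecutive measurements following the initial rise in ALT, AST or bilirubin"). It is also stopped for symptoms ("or if the patient develops symptoms of hepatotoxicity, subjects will be considered to have developed significant hepatotoxicity").

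**Section 6.6 decides what the DSMB sees of that tier.** Besides incident hepatotoxicities, the quarterly masked-group reports contain "counts of patients who required more frequent liver function testing due to" one stated cause. That cause is given as "rises in ALT levels of more than 1.5 times baseline ALT or beyond 250 U/L". On trends it says: "The DSMB will also examine the trends in ALT or AST levels for each patient who experiences a rise in ALT". No other section widens this count or this trend review.

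**The concern.** Section 6.6 appears to restate the 5.8.1.1 trigger but names only one of its markers. If the DSMB table is programmed from 6.6, a patient can be on weekly liver tests under the protocol's own rule and still be absent from the table meant to show such patients by treatment group.

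This count is the board's between-group view of liver signals that have not reached a stopping limit. An imbalance in AST or in mild conjugated hyperbilirubinaemia would be harder to see there than an imbalance in ALT. Section 5.8.1.1 treats bilirubin as a reason both for closer testing and for stopping, yet 6.6 has it in neither the count nor the trends.

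**Working it through.** There is no planned figure to reproduce. The check compares two rules. Thresholds come from 5.8.1.1 and 6.6; baseline values and ULNs are my assumptions, because the protocol gives none.

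**1. The rules side by side**

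| Element | 5.8.1.1 (weekly testing) | 6.6 (count) | 6.6 (trend review) |
|---|---|---|---|
| ALT | at least 1.5 × baseline *and* above 250 U/L | above 1.5 × baseline *or* above 250 U/L | yes |
| AST | same limits as ALT | not named | shown, but only if ALT rises |
| Bilirubin | total at least 1.5 mg/dL, at least half direct | not named | not shown |
| Symptoms | yes | not named | only if ALT rises |

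So 6.6 names 1 of 4 triggers.

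I read 6.6 generously: a patient on weekly testing is counted whenever ALT meets the 6.6 condition, even if ALT was not the trigger. A strict reading of the causal wording would leave out more.

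**2. ALT-triggered patients.** The trigger requires ALT above 250 U/L, which alone meets the 6.6 condition. Lost: 0.

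**3. AST window.**
- Lower bound: max(1.5 × baseline AST, 250). This is 250 U/L for any baseline up to 250 / 1.5 = 166.7 U/L, and 1.5 × baseline beyond that.
- Upper bound: min(10 × ULN, 500). At an assumed ULN of 35, 40 or 45 U/L this is 350, 400 or 450 U/L.

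**4. Bilirubin window.** Total bilirubin from 1.5 to below 2.5 mg/dL with at least half direct; 2.5 is the severe stop.

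**5. How far ALT can rise and the patient still go uncounted.** The ceiling is min(1.5 × baseline ALT, 250). For an assumed baseline of 60, 100 or 150 U/L it is 90, 150 or 225 U/L.

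**6. Illustrative patients (assumed values)**

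| Patient | Weekly testing | In the 6.6 count |
|---|---|---|
| AST 60 to 260, ALT 80 to 100 | yes | no (100 is below 1.5 × 80 = 120) |
| Bilirubin 1.8, direct 1.0; ALT 80 to 90 | yes (1.0 is at least 0.9) | no |
| ALT 100 to 260 | yes | yes |
| ALT 40 to 80 only | no | no: meets the ALT wording, but no extra testing required |
| ALT 240 to 260 only | no (260 is below 1.5 × 240 = 360) | no: same reason |

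The first two patients have some ALT rise, so they enter the trend review, where the second patient's bilirubin is still not shown. With no ALT rise, both would be outside that review as well.

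**7. The *or*.** The last two rows show that *or* admits nobody who is not already on extra testing. Nor can a wider condition remove anyone. It could even bring in a bilirubin-triggered patient whose ALT goes from 40 to 80, whom *and* would exclude.

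**8. Another parse of 5.8.1.1.** If bilirubin is an alternative only to the 250 U/L limb, a 1.5-fold enzyme rise is still needed. AST-triggered patients remain uncounted, as do patients with a 1.5-fold AST rise plus bilirubin. The mismatch does not depend on the parse.

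**9. Data.** ALT, AST, total and direct bilirubin are in the hepatic panel at all 16 follow-up visits (5.4 and Appendix 9.3).

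**The case against.** The strongest reply is that the DSMB is not confined to this count. It receives incident hepatotoxicities each quarter in the same sentence of 6.6, every serious adverse event as it occurs, quarterly adverse event summaries (5.12.2) and all unmaskings (5.13), and it may ask for further safety reports. Its written charge is not among the documents. Each patient's testing and stopping rules operate under 5.8.1.1 whatever the board is shown. All of this stands, and it limits the point to one table and one trend review.

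Symptom-triggered patients are a weak example. Under 5.8.1.1 symptoms of hepatotoxicity lead to classification as significant hepatotoxicity and to stopping; 5.13 then unmasks. Symptoms such as jaundice or vomiting are also adverse events, recorded whatever their attribution. These patients are largely covered.

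The opening condition of the weekly-testing sentence presupposes some ALT or AST elevation, and the trend review sets no size for the ALT rise. Many affected patients would therefore enter the trend review. That is fair, but it does not put them in the count or add bilirubin to the trends.

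The severe cholestatic jaundice case on pioglitazone in 3.3.2 might seem to show what would be missed. It does not: bilirubin peaked above 35 mg/dL, 14 times the 2.5 mg/dL severe stop, so such a patient would be reported as an incident hepatotoxicity.

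What these routes do not surface by themselves is a bilirubin-triggered patient who stabilises below 2.5 mg/dL, or an asymptomatic AST-triggered patient whose ALT and bilirubin do not keep rising. Either reaches the board only if an adverse event is recorded or the board asks.

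**Conclusion.** The point holds as a limited mismatch in safety reporting. Section 6.6, followed as written, can omit from the masked-group count AST-triggered patients, and bilirubin-triggered patients from 1.5 to below 2.5 mg/dL who stabilise, when ALT is neither above 1.5 times baseline nor above 250 U/L. Bilirubin is absent from the trend review, and a patient with no ALT rise is outside that review altogether.

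The thresholds and the zero loss of ALT-triggered patients follow from the text. The upper end of the AST window and the ALT ceilings rest on assumed ULNs and baselines. With no trigger rates in the protocol, the number of patients affected is unknown and may be small.

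A reader might infer that the DSMB is blind to liver injury not led by ALT, or that writing *or* for *and* drops patients. The documents support neither: other reports reach the board, and the *or* is a separate wording mismatch that causes no omission. Sample size, alpha and the primary analysis are not touched. Correction is worthwhile because it costs so little.

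**What to change.** Replace the ALT-specific description in 6.6 with a reference to 5.8.1.1, for example: *Each quarter the DSMB will receive, by masked treatment group, the number of patients placed on weekly liver testing under any criterion of section 5.8.1.1, by trigger (ALT, AST, bilirubin, symptoms), and will review ALT, AST and bilirubin over time for each of these patients.* Citing the criteria instead of paraphrasing them also removes the *or*/*and* discrepancy.

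The cost is a short edit to 6.6 and one extra DSMB table, with no new data collection.

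A separate clinical question should go to the hepatology lead and the DSMB: the continuing-rise stop in 5.8.1.1 accepts AST as the initial rise but names only ALT or bilirubin for the rise that follows. Whether AST belongs there concerns patient management, and the reporting fix does not depend on the answer.

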7.1. Overview

The study protocol, questionnaires, and consent forms will be submitted to each participating center's IRB. Sites which recruit patients will submit their recruitment materials to their IRB prior to use. A site may not initiate any patient contact about the PIVENS trial until the site has IRB approval for the trial. All study personnel must complete training in the Protection of Human Subjects per NIH guidelines. The proposed study anticipates recruiting a significant proportion of racial/ethnic minorities (African-Americans, Asian-Americans and Hispanics) as well as non-Hispanic white subjects.

7.2. Institutional Review board (IRB) approval

A site may not initiate patient activities in the PIVENS trial until the site has IRB approval for the trial. Consent forms must have IRB approval. Sites must provide the DCC with a copy of the initial IRB approval notice and subsequent renewals as well as copies of the IRB approved consent statements.

7.3. Informed consent

A prototype consent will be prepared for the trial for screening to determine eligibility with an affirmation of consent for randomization in the trial. Individual sites may add material but may not delete material thought to be necessary for informed consent. Clinics may reformat and reword information to conform to their local requirements. The patient must sign the consent to be eligible for the trial. The consent form will describe the purpose of the trial, the procedures to be followed, and the risks and benefits of participation. Copies of the signed consent forms will be given to the patient, and this fact will be documented in the patient's record.

9.2. Committees

- Steering Committee
- Executive Committee
- Database Committee
- Measures and Assessments Committee
- Pathology Committee
- Standards of Care Committee
- Pediatrics Committee
- Ancillary Studies Committee
- Presentations and Publications Committee
- Treatment Trial Protocol Committee
- Pilot and Feasibility Studies Committee

9.3. Data collection schedule

	5	g Follow-up visits Weeks from ron domination																	
A gaagement/Droopdure	C1	visit	s p7	2	4	0	12	16		eks f	rom	rando	mizati	ion 64	72	80	00	06	120
	51	52	KZ	2	4	o	12	10	24	32	40	40	50	04	12	00	00	90	120
Consent	Х		Х																
Baseline medical history	Х																		
Followup medical history					Х	Х		Х	Х	Х		Х		Х	Х	Х		Х	Х
AUDIT, Skinner alcohol question		А	S		•	•		•	•	•	·	•	•	•		•	•	•	
Review of concomitant drugs	Х		Х		Х	Х		Х	Х	х		Х		Х	Х	Х		Х	х
Review for adverse effects				Х	Х	Х	Х	Х	Х	Х	Х	Х	Х	Х	Х	Х	Х	Х	Х
Drug dispensing			Х		Х	Х		Х	Х	Х		Х		Х	Х	Х			
Review of study drug adherence	•	•			Х	Х	Х	Х	Х	Х	Х	Х	Х	Х	Х	Х	Х	Х	•
Physical exam (Detailed/Focused)	D	•			F	F		F	D	F		D		F	F	F	•	D	F
DEXA scan for body fat		Х																х	Х
Liver biopsy	x											•						X	
Block 98 nutrition questionnaire		X										X						X	X
Functional activity questionnaire	•	Х			•	•		•	•	•	•	Х				•	•	Х	Х
HR-OOL (SF-36)		Х										Х						Х	Х
Liver symptom questionnaire		Х										Х						Х	Х
OGTT with insulin and C-peptide	•	Х				•			•	•	·	Х				•	•	Х	Х
Labs																			
Fasting glucose	Х								Х						Х				
Fasting lipid profile	Х											Х						Х	Х
CBC	Х								Х			Х						Х	Х
Metabolic panel	Х								Х			Х						Х	
Hepatic panel		Х		Х	Х	Х	Х	Х	Х	Х	Х	Х	Х	Х	Х	Х	Х	Х	Х
GGT and prothrombin time	•	Х			•	·	•	•	•	•	•	Х	•	•	·	•	•	Х	•
HbA1c		Х										Х						Х	
Pregnancy test (females)	Х	Х	Х	Х	Х	X	Х	Х	Х	Х	Х	Х	Х	Х	Х	Х	Х	Х	Х
Microalbuminuria		Х										Х						Х	х
Serum, plasma for banking		X						X		X		X		X		X		X	X
Serum vitamin E (banked serum)	•	X	•		•	•	•		•	•	•	X	•	•	•		•	X	
Closeout form	•	•		•					•	•				•				•	Х

Note: Detailed (D) physical includes measurement of height, weight, waist, and hips; vital signs (temperature, heart rate, respiratory rate, blood pressure); triceps skin fold thickness, mid upper arm circumference; examination for scleral icterus and pedal edema and auscultation of the heart and lungs; general physical findings (hepatosplenomegaly, peripheral manifestations of liver disease, ascites, wasting, fetor).
 Focused (F) physical includes measurement of height, weight, waist, and hips; vital signs (temperature, heart rate, respiratory rate, blood pressure); examination for scleral icterus and pedal edema and auscultation of heart and lungs.

Metabolic panel: sodium, potassium, chloride, bicarbonate, calcium, phosphate, BUN, creatinine, uric acid, albumin, total protein. **Hepatic panel:** total bilirubin, direct bilirubin, AST, ALT, alkaline phosphatase.

Lipid profile: total cholesterol, triglyceride, LDL, HDL.

Fasting visits: S1, S2, 16, 24, 32, 48, 64, 72, 80, 96, and 120.

Safety visits: 2, 12, 40, 56, and 88.

Confidential, not for citation or distribution

53

9.4. Whole blood draw schedule: mL of blood to be drawn at screening and follow-up visits

Procedure	Study visit (wk)																		
	s1	s2	2	4	8	12	16	24	32	40	48	56	64	72	80	88	96	120	Total
Fasting glucose	5							5						5					15
Fasting lipid	5										5						5	5	20
GTT w/insulin		25									25						25	25	100
CBC	5							5			5						5	5	25
Metabolic panel	5							5			5						5		20
Hepatic panel		5	5	5	5	5	5	5	5	5	5	5	5	5	5	5	5	5	85
GGT, PT/INR		5									5						5		15
HbA1c		5									5						5		15
Plasma: TGF-beta		5									5						5	5	20
Serum: fibrosis		10									10						10	10	40
Serum: Vit E		5									5						5		15
Serum: banking		25					20		20		25		20		20		25	20	175
Genetics		20																	20
Other screening	40	•	•	•	•			•	•		•		•	•	•	•	•	•	40
Total	60	105	5	5	5	5	25	20	25	5	100	5	25	10	25	5	100	75	605

9.5. Glossary

3-NT	-	3-nitrotyrosine
AMA	-	antimitochondrial antibody
ANA	-	anti-nuclear antibody
AST	-	aspartate aminotransferase
ALT	-	alanine aminotransferase
anti-HBc	-	hepatitis B core antibody
anti-HBs	-	hepatitis B surface antibody
anti-HCV	-	hepatitis C virus antibody
BMI	-	body mass index (kg/m^2 ; calculated as the weight in kilograms divided by the square of the height in meters)
BUN	-	blood urea nitrogen
CHZ	_	chlorzoxazone
DCC	_	data coordinating center
DEXA	_	dual energy x-ray absorptiometry
DPP	_	Diabetes Prevention Program
DSMB	_	Data and Safety Monitoring Board
ERCP	-	endoscopic retrograde cholangiopancreatography
FDA	-	Food and Drug Administration
FFA	-	Free Fatty Acids
GGT	-	gamma glutamyl transferase
HBsAg	-	hepatitis B surface antigen
HCV	-	hepatitis C virus
HIPAA	-	Health Insurance Portability and Accountability Act
HOMA-IR	-	homeostasis model assessment method for insulin resistance (calculated as
		[fasting insulin (μ U/ml) * fasting glucose (mmol/L)]/22.5)
HRQOL	-	health-related quality of life
INR	-	international normalized ratio for prothrombin time; INR=(PT _{patient} /PT _{control mean}) ^{ISI} ,
		where ISI=International Sensitivity Index
MAR	-	missing at random
MRCP	-	magnetic resonance cholangiopancreatography
NAFL	-	nonalcoholic fatty liver
NAFLD	-	nonalcoholic fatty liver disease
NAS	-	NASH CRN NAFLD/NASH activity score
NASH	-	nonalcoholic steatohepatitis
NHANES	-	National Health and Nutrition Examination Survey
NIDDK	-	National Institute of Diabetes and Digestive and Kidney Diseases
NIH	-	National Institutes of Health
OGTT	-	oral glucose tolerance test
PCOS	-	polycystic ovary syndrome
PCP	-	primary care provider

55

PIVENS	-	Pioglitazone vs vitamin E vs placebo for the treatment of nondiabetic patients with NASH trial
PPARγ	-	peroxisome proliferator-activated receptor-gamma
SAE	-	serious adverse event
SAM-e	-	S-adenosyl methionine
TNF	-	tumor necrosis factor
TZD	-	thiazolidinedione
TBARS	-	thiobarbituric acid reacting substances
UDCA	-	ursodeoxycholic acid (aka, URSO)
ULN	-	upper limit of normal
URSO	-	ursodeoxycholic acid (aka, UDCA)

9.6. Document history

PIVENS trial protocol (28 June 2004)

PIVENS trial protocol (20 June 2005)

Numerous editorial and wording changes were made to the following sections:

§ Design synopsis:

Added "upper arm circumference" to secondary outcome measures

- §3.1 Design overview
 - Changed "Patients will be asked to remain in the NAFLD Database with annual follow-up visits after the trial has ended." to "Patients will be asked to participate in the NAFLD Database with annual follow-up visits after the trial has ended."
 - Changed "urine pregnancy test" to "pregnancy test" in this section and throughout; rationale was that some clinics may choose to do blood pregnancy tests
- §4.4 Run-in period
 - Changed "Any over-the-counter medication or herbal remedy that is being taken with an intent to improve hyperlipidemia will not be allowed for at least 3 months prior to randomization nor after randomization." to "Any over-the-counter medication or herbal remedy that is being taken with an intent to improve hyperlipidemia will not be allowed for at least 3 months prior to randomization and will be discouraged after randomization."
- §5.2 Screening and baseline data collection
 - Changed plasma glucose to serum glucose in this section and throughout
- §5.2 Screening visit 1
 - Added mid-upper arm circumference and respiratory rate to list of procedures
 - Changed "ceruloplasmin" to "ceruloplasmin (if less than 40 years old)"
 - Added iron overload to list of laboratory items
 - Moved GGT and prothrombin time to the s2 visit
 - Deleted globulin

§5.2 Screening visit 2

- Added GGT and prothrombin time to laboratory tests
- §5.3 Randomization visit
 - Deleted height, weight, vital signs, and brief interim medical history from the procedures to be completed at the randomization visit.
 - Changed, "The medication assignment will not be generated unless the check finds that the

NASH PIVENS 2\PIVENSProt\Manall_6	Confidential, not for
4:08 pm Wednesday, April 18, 2007/klc	citation or distribution

9. Appendices

patient is eligible." to "The medication assignment will not be generated unless the check finds that the patient is eligible, and the clinic staff indicate that they want to randomize the patient."

- Changed "medication kit" to "medication bottles"
- Added option of sending study medication to clinical coordinator, if not using a research pharmacy
- § 5.4 Follow-up visits, Week 2 visit
 - Deleted interim history, height, weight, vital signs, and focused physical examination
- § 5.4 Follow-up visits, Week 4 visit
 - Changed "Interim history" to "Follow-up medical history" here and throughout
 - Added interim drinking history
 - Added respiratory rate to vital signs
 - Added liver symptoms to items included in focused physical examination
 - Added "Dispense study drug and review study drug adherence with patient"
- § 5.4 Follow-up visits, Week 8 visit
 - Added interim drinking history
 - Added respiratory rate to vital signs
 - Added liver symptoms to items included in focused physical examination
 - Added "Dispense study drug and reviw study drug adherence with patient"
- § 5.4 Follow-up visits, Week 12 visit
 - Deleted Follow-up medical history
 - Added "Dispense study drug and review study drug adherence with patient"

§ 5.4 Follow-up visits, Week 16 visit

- Added interim drinking history
- Added respiratory rate to vital signs
- Added liver symptoms to items included in focused physical examination
- Added "Dispense study drug and review study drug adherence with patient"
- § 5.4 Follow-up visits, Week 24 visit
 - Added interim drinking history
 - Added respiratory rate to vital signs
 - Added waist and hip measurements, triceps skin fold, mid-upper arm circumference, and liver symptoms to list of procedures in detailed physical examination
 - Added "Dispense study drug and review study drug adherence with patient"

§ 5.4 Follow-up visits, Week 32 visit

- Added interim drinking history
- Added respiratory rate to vital signs

NASH PIVENS 2\PIVENSProt\Manall_6 4:08 pm Wednesday, April 18, 2007/klc

- Added liver symptoms to items included in focused physical examination
- Added "Dispense study drug and review study drug adherence with patient"
- § 5.4 Follow-up visits, Week 40 visit
 - Deleted Follow-up medical history
 - Added "Review study drug adherence with patient"
- § 5.4 Follow-up visits, Week 48 visit
 - Added interim drinking history
 - Added respiratory rate to vital signs
 - Added waist and hip measurements, triceps skin fold, mid-upper arm circumference, and liver symptoms to list of procedures in detailed physical examination
 - Added "Dispense study drug and review study drug adherence with patient"

§ 5.4 Follow-up visits, Week 56 visit

- Deleted Follow-up medical history
- Added "Review study drug adherence with patient"
- § 5.4 Follow-up visits, Week 64 visit
 - Added interim drinking history
 - Added respiratory rate to vital signs
 - Added liver symptoms to items included in focused physical examination
 - Added "Dispense study drug and review study drug adherence with patient"

§ 5.4 Follow-up visits, Week 72 visit

- Added interim drinking history
- Added respiratory rate to vital signs
- Added liver symptoms to items included in focused physical examination
- Added "Dispense study drug and review study drug adherence with patient"
- § 5.4 Follow-up visits, Week 80 visit
 - Added interim drinking history
 - Added respiratory rate to vital signs
 - Added liver symptoms to items included in focused physical examination
 - Added "Dispense study drug and review study drug adherence with patient"

§ 5.4 Follow-up visits, Week 88 visit

- Deleted Follow-up medical history
- Added "Review study drug adherence with patient"
- § 5.4 Follow-up visits, Week 96 visit
 - Added interim drinking history

NASH PIVENS 2\PIVENSProt\Manall_6 4:08 pm Wednesday, April 18, 2007/klc

- Added respiratory rate to vital signs
- Added waist and hip measurements, triceps skin fold, mid-upper arm circumference, and liver symptoms to list of procedures in detailed physical examination
- Added "Dispense study drug and review study drug adherence with patient"
- § 5.4 Follow-up visits, Week 120 visit
 - Added interim drinking history
 - Added respiratory rate to vital signs
- § 5.5 Standardized questionnaires Alcohol questionnaires
 - Clarified that the interim alcohol questionnaire is included in the Follow-up medical history form, and is not a separate form
- § 5.7 Overview of scoring of liver biopsies
 - Under (3) Fibrosis based upon Masson's trichrome stain as 0-4, added "perisinusoidal" to 1a and 1b
 - Under (9), changed "Iron as 0 to 4" to "Hepatocellular iron grade based on iron stain as 0 (absent or barely discernible, 40x), 1 (barely discernable granules, 20x), 2 (discrete granules resolved, 10x), 3 (discrete granules resolves, 4x), and 4 (masses visible by naked eye)"
- § 9.3 Data collection schedule was revised
- § 9.4 Whole blood draw schedule was revised
- § 9.5 Glossary
 - Added definition of AMA

PIVENS trial protocol (13 July 2006)

Following changes were made to sections below:

§ Design synopsis:

Deleted exclusion criteria - "Men of childbearing potential: unwillingness to use an effective form of birth control during the trial"

§ 4.2 Inclusion criteria:

Clarified wording on process for additional pathologist review in cases of NAS=4.

§ 4.3 Exclusion criteria:

Deleted Criterion #24. Men of childbearing potential: unwillingness to use an effective form of birth control during the trial

§ 5.4 Follow-up visits

Week 4 visit: added waist, hip measurements

Week 8 visit: added waist, hip measurements Week 16 visit: added waist, hip measurements Week 32 visit: added waist, hip measurements Week 64 visit: added waist, hip measurements Week 72 visit: added waist, hip measurements Week 80 visit: added waist, hip measurements Week 120 visit: added waist, hip measurements

- § 9.3 Data collection schedule was revised to include waist and hip measurements in focused physical examination
- § 6.2 Outcome measures Clarified wording on process for additional pathologist review in cases of NAS=4

PIVENS Trial Protocol (18 April 2007)

- §5.4 Follow-up visits Week 120 visit: added DEXA scan for body composition; added blood draw for serum and plasma banking at central repository
- \$5.6 Specimen repository added week 120 visit to blood collection schedule
- \$9.3 Data collection schedule: added DEXA scan, blood draw for serum and plasma banking, and closeout form at f120 visit
- §9.4 Whole blood draw schedule: added blood draw for serum and plasma banking at f120 visit
